### Overall Clinical Grade:

Grade 0 No stage 1-4 of any organ

Grade I Stage 1-2 skin and no liver or GI involvement

Grade II Stage 3 skin and/or Stage 1 liver and/or Stage 1 GI

Grade III Stage 0-3 skin with Stage 2-3 liver and/or Stage 2-3 GI

Grade IV      Stage 4 in any target organ (skin, liver, GI)

### **Minnesota Risk Scoring:**

#### **Standard Risk:**

Stage 1-3 skin (single organ system)

Stage 1 GI (single organ system)

Stage 2 lower GI (if upper GI is absent)

Stage 1 upper GI + Stage 1-2 lower GI

Stage 1-3 skin + Stage 1 GI (two organ system involvement)

Stage 1-3 skin + Stage 1-4 liver (two organ system involvement)

**High Risk:** Any other combination of single or dual organ aGVHD stages

**Minnesota risk scoring calculator:** <http://z.umn.edu/MNAcuteGVHDRiskScore>

## **9.1      Endpoint and Response Criteria**

### **9.1.1      Definitions**

**Treatment Response** is defined as a patient's weekly clinical GVHD response due to systemic treatment, typically systemic steroids, without taking into account if new lines of treatment were given.

**Study Response** is defined as a patient's day 28 clinical GVHD response due to systemic treatment, with also taking into account if new lines of treatment were given.

**Complete Response (CR):** All evaluable organs (skin, liver, GI tract) stage 0. For a response to be scored as CR on day 28, the patient must be in CR on that day and have had no intervening additional GVHD therapy.

**Partial Response (PR):** An improvement in one or more organ involved with GVHD symptoms without worsening in others. For a response to be scored as PR on day 28, the patient must be in PR on that day and have had no intervening additional GVHD therapy.

**Very Good Partial Response (VGPR):** Any response that approximates a CR with the exception of rash <25% body surface area. For a response to be scored as VGPR on day 28, the patient must be in response on day 28 and have had no intervening systemic therapy for acute GVHD other than steroids.

**No response (NR):** All responses that are not CR, PR, or VGPR. Patients who receive any systemic GVHD therapy other than the continuation or modification of GVHD prophylaxis, systemic steroids, and topical/non-absorbable oral steroid therapy, will be scored as NR on day 28 regardless of organ staging.

### **9.1.2      Earliest response**

Earliest response, or first response, is defined as the first date from start of systemic treatment when CR, PR or VGPR occurs. Further improvement may

occur, but the initial date of response will be reported and used to determine duration of response

#### **9.1.3 Steroid refractory GVHD**

Steroid refractory GVHD is defined as either an increase by at least one GVHD stage that requires initiation of an additional line of therapy beyond steroids or a lack of response (i.e., NR) by day 28. Escalation of steroid doses during treatment for GVHD are not considered in the definition of steroid refractory GVHD. The resumption or addition of tacrolimus, sirolimus, or cyclosporine will not be considered a new line of treatment.

#### **9.1.4 GVHD Flare**

An increase in GVHD symptoms of at least 1 stage after CR, PR or VGPR on day 28 that requires a change in treatment. Change in treatment includes increase in steroid dose of  $>0.25$  mg/kg/day or initiation of another systemic immunosuppressive therapy. The resumption or addition of tacrolimus, sirolimus, or cyclosporine will not be considered a new line of treatment.

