### 3.5 Serial Monitoring Identifies Patients with Ultra-Low Risk GVHD

Given that the MAP can also act as a monitoring biomarker, we used both the clinical response and the MAP during the first two weeks of systemic steroid treatment to analyze 85 pediatric patients with Minnesota standard risk/AA1 GVHD. MAPs were categorized as high or low using the validated 0.29 threshold. Changes in clinical severity were scored as either response, stable, or progression. Patients who responded by the end of week one and maintained both clinical response and a low MAP at week two (48% of patients), experienced 95% day 28 ORR. Importantly, serial monitoring demonstrated that **slow** clinical responders (17% of patients) have equally good outcomes with a 100% ORR; these patients have stable disease at week one, a response at week two and a low MAP at all three assessments. The remaining patients (35%) either lacked a treatment response or had an increase in their MAP above 0.29. Taken together, serial monitoring identifies 65% of patients with Minnesota standard risk/AA1 GVHD as an **ultra-low risk** group with higher response rates (96% vs 47%, p<0.001) than other patients. Furthermore, GVHD flares that required an increase in treatment occurred in only 5% of patients with ultra-low risk GVHD. Thus, these patients are excellent candidates for a GVHD treatment strategy that minimizes steroid exposure.

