#### **9.1.5 Duration of response**

Duration of response is calculated as the number of days from first response to steroid treatment until GVHD flare, development of steroid refractory GVHD, initiation of additional systemic treatment for GVHD, or death, whichever comes first.

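### A GVHD flare needs a prior day-28 response, so a taper-period flare rescued with steroids alone does not end duration of response

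*Combined protocol and SAP*

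**What the plan says.** All references are to the combined protocol and SAP.

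- **Flare (9.1.4):** "An increase in GVHD symptoms of at least 1 stage after CR, PR or VGPR on day 28 that requires a change in treatment". The qualifying change is a steroid increase of more than 0.25 mg/kg/day "or initiation of another systemic immunosuppressive therapy".
- **Start of the clock (9.1.2):** first response is "the first date from start of systemic treatment when CR, PR or VGPR occurs", and "the initial date of response will be reported and used to determine duration of response".
- **End of the clock (9.1.5):** "Duration of response is calculated as the number of days from first response to steroid treatment until GVHD flare, development of steroid refractory GVHD", additional systemic GVHD treatment, or death, whichever is earliest.
- **Steroid-refractory GVHD (9.1.3):** either a stage increase that needs a line of therapy beyond steroids, or non-response by day 28. "Escalation of steroid doses during treatment for GVHD are not considered in the definition of steroid refractory GVHD".
- **Lines of therapy (9.1.7):** only systemic immunosuppression added to steroids counts as second line.
- **Table 1 (7.1):** week-1 responders are sorted at week 2 into responder, partial loss of response, or flare. The flare row leaves the taper schedule for a higher suggested dose.
- **Background (3.5):** "GVHD flares that required an increase in treatment occurred in only 5% of patients with ultra-low risk GVHD". No time window or flare definition is attached to that figure.

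Duration of response is secondary objective 4.2.2. Section 14.2 lists it among the outcomes that decide whether to proceed to phase III, and 14.3 plans to compare it with historical controls.

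**The concern.** The clock can start three weeks before one of its own end events becomes possible. Those weeks are the protocol taper, and whether an early response lasts through a fast taper is what the trial sets out to learn: section 3.9 says physicians delay tapers because they doubt that early responses are durable.

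The term is also used inconsistently. Table 1 assigns children to a flare category at week 2, although under 9.1.4 no flare can exist then. An analyst who follows section 9.1 literally would ignore an event that the treatment schema names and acts on. If the children so affected are treated with steroids alone, which is the route that Table 1 and 7.1.10 suggest, their responses are recorded as continuous. The error runs in one direction, towards longer durations.

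**Working it through.** **1. Trace one child through the definitions.** Assume first response on day 7, a stage increase on day 14 treated only with a steroid increase above 0.25 mg/kg/day, PR on day 28, and no later event.

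| Possible end event | Source | Triggered on day 14? |
|---|---|---|
| Flare | 9.1.4 | No: it does not follow a day-28 response |
| Steroid-refractory GVHD | 9.1.3 | No: escalation is excluded, and the child is not NR by day 28 |
| Additional systemic treatment | 9.1.5, 9.1.7 | No: nothing was added to steroids |
| Death | 9.1.5 | No |

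The day-28 response is also unaffected. Section 4.5 bars only systemic therapy other than steroids, and the NR definition in 9.1.1 exempts systemic steroids.

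**2. Duration of response for that child** (end of observation is an assumption: day 90 or day 365).

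- Current text, to day 90: 90 − 7 = **83 days**
- Current text, to day 365: 365 − 7 = **358 days**
- Flare recognised at any time after first response: 14 − 7 = **7 days**

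**3. Does the primary endpoint catch these children?** Its dose limit is 13.5 mg/kg over the first four weeks (4.4). First reproduce the total in Table 1 for the fastest taper, using seven daily doses at each of the first four dose levels in that row: 7 × (0.5 + 0.35 + 0.25 + 0.15) = 8.75 mg/kg, which matches. Cumulative dose before day 21 is 7 × (0.5 + 0.35 + 0.25) = 7.70. The escalations below illustrate the arithmetic only; each is held through the 28 daily doses.

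| Escalation | Sum | Total, mg/kg | Against 13.5 |
|---|---|---|---|
| 1 mg/kg/day from day 14 | 3.5 + 2.45 + 14 × 1 | 19.95 | fails |
| 1 mg/kg/day from day 21 | 7.70 + 7 × 1 | 14.70 | fails |
| 1 mg/kg/day from day 23 | 7.70 + 2 × 0.15 + 5 × 1 | 13.00 | passes |
| 0.55 mg/kg/day from day 21 | 7.70 + 7 × 0.55 | 11.55 | passes |

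The last row is a rise of 0.55 − 0.25 = 0.30 over the preceding dose, or 0.55 − 0.15 = 0.40 over the scheduled one. Either exceeds the 0.25 threshold in 9.1.4. In the last two rows, a child in response on day 28 is a primary success and also has an unbroken duration of response.

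**4. Design quantities.** The 90% power in 14.2 reproduces: with N = 50 and a two-sided exact test at 0.001, rejection at 17 or more successes gives power 0.9025 at 42%. Nothing in this point alters it.

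**The case against.** The case for leaving the text alone has several sound parts.

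- **Much taper-period worsening still ends response.** A reader might infer that every flare before day 28 is lost to duration of response. That is not so: second-line systemic therapy, NR by day 28 and death all end it. Table 1 sends flares to discretionary treatment or a clinical trial, so some will receive a second agent. The gap is confined to steroid-only rescue with response regained by day 28.
- **There is no flare-rate endpoint.** None is listed in 4.2, 4.5 to 4.7, 14.1 or 14.3. Flare enters the analysis only through duration of response.
- **The events are recorded.** Weekly staging, doses, ad hoc dose changes and reasons for increases are collected, and cumulative dose at days 28 and 90 reflects any escalation. Most early escalations also fail the primary endpoint on dose.
- **Safety monitoring is separate.** Section 10.6 names steroid-refractory GVHD as the primary risk of the taper and gives it its own stopping rule, which this wording does not touch.
- **The ultra-low-risk subset is less exposed.** Under 3.5, membership requires a response maintained or reached at week 2, so week-2 flares fall outside it. Its unobserved window is roughly days 14 to 28.
- **Deleting three words is not enough.** Table 1 distinguishes partial loss of response from flare by comparison with baseline; 9.1.4 uses a one-stage rise plus a treatment change.

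All of this stands and limits the point. None of it supplies an end event for the child in step 1 of the working.

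**Conclusion.** The definitions conflict, and the conflict biases duration of response upward for responders who worsen during the taper, are rescued with steroids alone and are in response on day 28. For the worked child the recorded value is 83 or 358 days instead of 7. This rests on reading 9.1.4 literally and on the assumed course and follow-up of that child.

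How many children are affected cannot be computed, because the documents give no taper-period flare rate. A reader might set an assumed count against the 5% in 3.5 and report a shortfall in percentage points. The documents do not support that: the 5% applies only to ultra-low-risk patients, has no stated window or definition, and is not used in any planned comparison. For scale only, 5% of the 33 ultra-low-risk children expected in 14.3 is about 1.7.

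Nor does the point undermine the primary endpoint. Its definition is unchanged, and the late or small escalations that pass its dose limit meet it as written. This should be fixed before duration of response is analysed, but it does not threaten the trial's main conclusion.

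**What to change.** 1. For the duration-of-response analysis, define flare as an increase of at least one stage at any time after the first CR, PR or VGPR that meets the change-in-treatment criterion already in 9.1.4. State explicitly that a qualifying steroid-only escalation ends response.
2. Reconcile the term with the flare and partial-loss rows of Table 1, without changing any dosing rule. The scheduled partial-loss path holds the dose at 0.35 mg/kg/day, so it would not meet the 0.25 threshold. A discretionary increase under 7.1.11 could, and the text should say how such a case is classified.
3. State whether the flare-triggered staging and serum collection in Table 2 applies before day 28.
4. Apply the same definition to the historical cohort where its data allow, and say so where they do not.

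The staging and dose data needed are already collected. The costs are a short amendment, possibly some added flare samples depending on item 3, and a less favourable reported duration of response.

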#### **9.1.5 Duration of response**

Duration of response is calculated as the number of days from first response to steroid treatment until GVHD flare, development of steroid refractory GVHD, initiation of additional systemic treatment for GVHD, or death, whichever comes first.

#### **9.1.6 Steroid discontinuation**

The date of discontinuation of steroid therapy will be reported.

#### **9.1.7 Lines of GVHD therapy**

Any additional systemic immunosuppression treatment to steroid therapy for acute GVHD will be considered 2nd line therapy and considered a failure to respond to steroid treatment. Resumption or changes in GVHD prophylaxis (e.g., substitution of mycophenolate for tacrolimus due to PRES) are not considered new lines of therapy. The addition of tacrolimus, sirolimus, or cyclosporine will not be considered a new line of treatment. Topical steroids and non-absorbable oral steroids are not considered new lines of therapy.

#### **9.1.8 Non-Relapse Mortality (NRM)**

Any death that occurs after HCT not attributable to relapse of the underlying disease will be considered a non-relapse death.

#### **9.1.9 Chronic GVHD**

The occurrence of chronic GVHD as defined by NIH consensus criteria requiring systemic treatment, including date of diagnosis, will be reported.

#### **9.1.10 Relapse**

Relapse, including date of relapse, of the underlying malignancy will be reported.

#### 9.1.11 Serious Infections

Serious infections are defined using the standardized criteria widely used for clinical trials at academic BMT centers, such as life-threatening fungal infections or hemorrhagic cystitis from BK viral infection and include clinically significant CMV infections that require anti-viral treatment regardless of end-organ damage, given the toxicity of such treatments. Serious infections include any viral, bacterial, fungal or parasitic infections that requires systemic treatment.

All grade 2 or 3 infections as defined by the Blood and Marrow Transplant Clinical Trials Network must be reported through day 90.

9.1.12 **Linear growth velocity:** The change in linear growth (height) from baseline to last contact, corrected for age and duration of observation.

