### 3.3 Steroid Treatment Toxicities

Steroid treatment causes chronic physical complications and reduces QOL that correlate with cumulative steroid exposure. Children are particularly susceptible to these complications. For example, corticosteroids are potent inhibitors of linear growth, especially during the adolescent growth spurt. Likewise, the incidence of corticosteroid-related osteonecrosis, a debilitating skeletal complication, is highest in adolescents, presumably reflective of the vulnerability of rapidly growing bone. Acute complications of steroid treatment are less well studied but include more infections and reduced QOL. Serious infections correlate with other steroid toxicities and thus can serve as a surrogate for overall steroid morbidity. We quantified the risk of serious infections using data from 176 adult and pediatric MAGIC natural history trial patients with Minnesota standard risk GVHD that was low risk by biomarkers (see below). Serious infections were defined using the standardized criteria widely used for clinical trials at academic BMT centers, such as life-threatening fungal infections or hemorrhagic cystitis from BK viral infection and included clinically significant CMV infections that required anti-viral treatment

regardless of end-organ damage, given the toxicity of such treatments. Systemic steroid treatment doubled the incidence of serious infections (56% vs 30%,  $p=0.002$ ), a finding driven by serious viral infections (e.g., CMV colitis, HHV6 encephalitis, EBV-related PTLN, etc.) (42% vs 19%,  $p=0.003$ ) [Figure 1]. The difference in serious infections remained statistically significant when we controlled for severity of target organ involvement ( $p=0.01$ ).

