### **14.3 Data Analysis Plans**

The primary endpoint is the proportion of patients who (1) achieve CR, VGPR, or PR by day 28 of treatment without additional immunosuppressive therapy and (2) whose cumulative prednisone exposure is  $\leq 13.5$  mg/kg. The proportion of patients who are successfully treated with  $\leq 13.5$  mg/kg cumulative prednisone dose will be compared to the historical control rate of 14% using a Chi-squared test.

All study patients will be analyzed and when appropriate, subset analyses by ultra-low risk and other patients will be performed. We expect 33 ultra-low risk patients and 17 other patients out of our sample size of 50 study patients, which will be sufficient for subset analyses.

Secondary outcomes such as the overall response rate, duration of response, cumulative incidence of steroid-refractory GVHD, incidence of serious infections (viral, bacterial, fungal, and parasite), cumulative steroid exposure at day 28 and day 90, overall survival at 6 and 12 months, cumulative incidence of NRM at 6 and 12 months, relapse rate at 6 and 12 months, and cumulative incidence of chronic GVHD requiring systemic steroid treatment by one year will be estimated and compared to historical controls.

Continuous variables will be summarized using standard summary statistics such as number of observations (n), mean, standard deviation (SD), minimum and maximum values, median, and 1st and 3rd quartiles. Categorical variables will be summarized in frequency tables as counts and percentages.

Cumulative incidence of non-relapse mortality will be estimated by Gray's method and relapse will be considered as a competing risk. Disease free and overall survival, defined as the time from the transplantation to death or to last follow-up if alive, will be estimated by the method of Kaplan-Meier and the probability curves and 95% confidence intervals will be provided based on the method of Brookmeyer and Crowley.

The exploratory endpoints of linear growth velocity and patient reported outcomes as per Appendix B will be described for patients whose cumulative steroid exposure is  $\leq 13.5$  mg/kg and  $> 13.5$  mg/kg. Linear growth velocity will be expressed as a standard deviation score of the sex- and age-specific mean.

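### Read literally, the trial's serious-infection definition is wider than the one behind the only historical rates, and nothing aligns them before the planned comparison

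*Combined protocol and SAP*

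**What the plan says.** Section 3.3 gives the preliminary infection data. They come from "176 adult and pediatric MAGIC natural history trial patients" with Minnesota standard risk, biomarker low-risk GVHD. The definition there has two parts. The base is: "Serious infections were defined using the standardized criteria widely used for clinical trials at academic BMT centers." The one treatment-based extension is that the definition "included clinically significant CMV infections that required anti-viral treatment", whether or not an organ was damaged, on the ground that those treatments are toxic. The overall rates are 56% with systemic steroids and 30% without (p=0.002); the viral rates are 42% and 19%.

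Section 9.1.11 restates both parts with the same two citations and adds a sentence: "Serious infections include any viral, bacterial, fungal or parasitic infections that requires systemic treatment." A reporting instruction follows: "All grade 2 or 3 infections as defined by the Blood and Marrow Transplant Clinical Trials Network must be reported through day 90."

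Section 4.5 (item 2) ties the secondary endpoint to Section 9.1.11. Section 8.2 and Table 2 set monitoring and reporting of infections as defined there, through day 90. Section 14.3 lists the incidence of serious infections among the secondary outcomes that "will be estimated and compared to historical controls". Section 14.2 makes serious infections one input to the decision on a phase III trial and to continuous futility monitoring.

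**The concern.** A historical comparison is only as good as the match between the two event definitions. Here the trial's definition contains a clause that the definition behind the preliminary data lacks. A child who meets the endpoint only because an infection was treated systemically counts in the trial, but a similar patient would not have counted in the preliminary data. The error runs one way: it can add events to the trial and cannot remove any.

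Section 3.3 treats serious infection as a surrogate for overall steroid morbidity, which is the harm that the taper is meant to reduce. If the taper lowers infections but the trial counts more kinds of infection than its control, the benefit could shrink or vanish in the reported comparison, and Section 14.2 would carry that result into the phase III decision.

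**Working it through.** **1. The two definitions side by side.**

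| Element | Section 3.3 (preliminary data) | Section 9.1.11 (trial endpoint) |
|---|---|---|
| Standardized transplant-trial criteria | yes | yes |
| Clinically significant CMV needing antiviral treatment | yes, added explicitly | yes |
| Any infection needing systemic treatment | absent | present |
| Observation window | all first serious infections fell within 90 days (Section 8.2) | day 90 |

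The window matches; the third row does not. The CMV clause suggests that the third row matters. If treatment alone already qualified under the base criteria, there would have been no need to add treated CMV and justify it. Under the added sentence, the CMV clause becomes redundant.

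**2. The plan's own figures.** The plan states no control rate, test, alpha or power for infections. Its only power statement is for the primary endpoint (14% against 42%, n=50, two-sided exact, alpha 0.001). That reproduces: reject at 17 or more of 50, attained upper tail 0.00029, power 0.9025. The split of the 176 patients by steroid use is not given, but the infection figures are coherent. With an assumed split of 120 and 56, 67/120 against 17/56 gives a Fisher p of 0.002, as stated.

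**3. Points per child.** Let r be the true trial rate on the Section 3.3 definition and k the number of children counted only through the added sentence. The expected reported rate is r + k/50, so each such child adds 1/50 = 2 points. The number that fully masks a fall from 56% to r is k = 50 × (0.56 − r):

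- r = 30% (the rate without systemic steroids in Section 3.3): 50 × 0.26 = 13 children.
- r = 40% (illustrative only): 50 × 0.16 = 8 children.

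**4. Effect on the chance of showing a reduction.** Assumptions, none of them in the plan: a fixed control rate of 56%, an exact binomial test, two-sided 0.05. Since P(X ≤ 20 | 50, 0.56) = 0.0166, a significant reduction needs 20 or fewer events. The chance is P(X ≤ 20 | 50, r + x), where x = k/50 is the assumed excess:

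| r | x = 0 | 5 points | 10 points | 15 points | 20 points |
|---|---|---|---|---|---|
| 30% | 0.95 | 0.81 | 0.56 | 0.29 | 0.10 |
| 35% | 0.81 | 0.56 | 0.29 | 0.10 | 0.02 |
| 40% | 0.56 | 0.29 | 0.10 | 0.02 | <0.01 |

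**5. Sensitivity.** If 56% is instead treated as an estimate from 88 to 140 steroid-treated patients (assumed), the chance at expected reported rates of 30%, 40% and 50% is 0.85 to 0.90, 0.44 to 0.49 and 0.10 to 0.11. The pattern is the same.

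**The case against.** The case against has several parts, and much of it stands.

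- *The added sentence may only list organism classes*, in line with Sections 4.2.3 and 4.5. That may be the intent, but the wording makes systemic treatment a sufficient condition. If a list was meant, the sentence should say so.
- *How much wider the definition is depends on a source outside the document.* This stands. Both sections cite the same severity grading table, which is not reproduced. An infection needing systemic treatment may often meet the standardized criteria anyway. The CMV clause points the other way, but that is an inference.
- *The control is not named.* This stands. A reader might infer that 56% from the pooled cohort will be the comparator; Section 14.3 names no rate or cohort. Section 3.2 describes natural-history data on 250 children with treated GVHD, so a pediatric control set is conceivable. But the Section 3.3 rates are the only infection rates given, and no section plans to re-score any control.
- *Collection is not restricted.* A reader might infer that sites report only grade 2 or 3 infections, so that the data could not support the endpoint. The text does not say that. The grade 2 or 3 instruction is a minimum, and Table 2 has everything defined in Section 9.1.11 reported.
- *The consequence is limited.* This stands. The phase III decision combines several outcomes with no infection threshold, and the definitional mismatch cannot create a false claim of fewer infections.

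**Conclusion.** The definitions differ on their face, and the plan neither aligns them nor names the control. If the Section 3.3 data, or controls scored the same way, are used, the mismatch can only raise the trial rate relative to the control and so can hide a reduction. The size per child is fixed at 2 points; the number of such children cannot be derived from the document. The tables above show what an excess of a given size would do, not that an excess of that size exists. They also rest on an assumed test, alpha and comparator.

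The mix of adults and children in the 176 is a second source of non-comparability for a trial of ages 0 to 21; its direction is unknown. A reader might conclude that the infection comparison is bound to fail or that the trial's main result is in doubt. Neither follows. The endpoint is secondary, and the primary test and its power do not depend on it. This should be corrected before analysis, at little cost.

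**What to change.** Use one identical definition, through day 90, for trial and control patients in the comparison. Either route works:

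- Use the Section 3.3 definition (standardized criteria plus clinically significant CMV requiring treatment) in both groups, and report the count of all systemically treated infections as a separate descriptive line; or
- Keep Section 9.1.11 as written and re-score the controls under it. This needs control data on treated infections outside the standardized criteria, and the document does not say whether these were recorded.

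If the added sentence was meant only to list organism classes, reword it so that systemic treatment is not a qualifying criterion by itself.

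In Section 14.3, name the control: pediatric, systemically treated Minnesota standard risk/Ann Arbor 1 MAGIC patients, with their number, rate and confidence interval, and the method of comparison.

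The cost is a short edit to Sections 9.1.11 and 14.3, a re-tabulation of existing data and some precision. With 56% as a stand-in rate, the 95% half-width is 1.96 × √(0.56 × 0.44 / m). That is about 8 to 10 points for m of 140 down to 88 pooled steroid-treated patients (assumed). It is about 11 points for m = 85, if the 85 children analysed in Section 3.5 were the control set and all had infection data (also assumed).
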